- How is spending managed over time to ensure that there is enough money at the end of each financial year?
- How is spending managed against contracts [where relevant: i.e. cost and volume and cost per case but not block contracts]
 - How have the GPs in the site discussed resource allocation?
- How do you think you will deal with the cost of very expensive cases? Have you discussed with the HA/HC/FHSA?
- F3. [Risk Management] What arrangements, if any, have been made for a contingency reserve?

SECTION G: COSTS OF THE NEW TP STRUCTURE

- G1. TP involves additional work for you, your GP colleagues and practice staff. Where is this extra work coming from? [information gathering? contracting? risk management? co-rdination/liaison?]
 - What problems does this cause?
 - What subsidy, in cash or in kind, have you had from the HA/HC/FHSA apart from the £20k allowance provided by Region?

Last Question

• In practice, what would you say the key tasks of your TP site are for the next 6 months?

END OF INTERVIEW

End of Questionnaire Responsibilities

- 1. Thank the interviewee
- 2. Ask for personal details of interviewee (for front of questionnaire)
- 3. Tell the interviewee broadly what happens in the future (CATIs, further visits etc.)
- 4. Ask if interviewee would like to ask anything about the evaluation.
- 5. Using the analysis guide, write a report on the interview a.s.a.p. using your notes, and the tape recording, to help you.

ANNEXE 3

NOT FOR USE WITHOUT PERMISSION OF TP RESEARCH CONSORTIUM

STAFF PERCEPTIONS OF COST AND BENEFIT OF TP USING A DIARY CARD

The brief for the evaluation refers to a number of operational issues including the 'the administrative workload for the practices and members of the team'. Previous work in the Scottish fundholding evaluation by a member of the current team showed that, using a simple diary method of assessing time spent, lead doctors worked an average of 7.9 hours/day as against 7.2 hours per day for non-lead doctors and that this included an extra hour per day for administration (3.0 against 2.1 hours) associated with less time for 'breaks' during the day (0.6 hours against 1.0 hours).

Similarly, when participating doctors and budget clerks/managers were asked to indicate their perceptions of the global perceived costs and benefits of being fundholders on a 10-point analogue scale (extremes 'none' and 'a lot') lead general practitioners reported both higher costs and higher benefits than did non-lead general practitioners, while budget clerks/managers reported the highest perceived costs, and benefits intermediate between the two groups of doctors. By the end of the year studied, it appeared that perceived benefits were about to exceed perceived costs for lead doctors and for non-lead doctors and that the gap between costs and benefits for clerks and managers was narrowing.

Specific Questions

- 1. What are the relative perceptions of global costs and benefits held by lead doctors, non-lead doctors and budget managers in standard fundholding practices after the settling-in year has passed?
- 2. Will the first year of TP produce increases in perceived costs over benefits for participating doctors and administrators?
- 3. After the first year of TP, will the perceptions of costs and benefits in TPP and SFH practices be different?

The hypothesis is that, after a settling-in period, perceptions of benefit will exceed those in costs in both TPP and SFH practices, that the start-up relation between costs and benefits in TPP practices may initially be unfavourable, and that larger term perceptions of benefits to costs may be greater in TPP than in SFH practices.

Method

The diary card used to collect information on perceived costs and benefits in the Edinburgh fundholding project will be adapted for use in this part of the evaluation. The global 1-10 analogue scale for costs and benefits will be used on one side of the record card, and appropriate additional questions covering time spent on administrative and developmental work on TP - which may vary as the project develops - will be included on the reverse side.

All lead GPs, TP site managers and health commission TPP leads at all sites will be asked to complete cards at the end of each week throughout the study. In addition, all partners in one practice with 10,000-15,000 patients at each of 6 TPP sites and in one practice with 6,000 patients or less at each of 6 TPP sites, will be asked to complete weekly diary cards. Furthermore, each month all respondents will be asked to fill in a critical incident card giving information on significant positive and negative experiences of TP.

ANNEXE 4 NOT FOR USE WITHOUT PERMISSION OF TP RESEARCH CONSORTIUM

DRAFT ANALYSIS FRAMEWORK FOR FACE-TO-FACE INTERVIEW WITH TPP SITE LEAD GPs

EXPLANATORY NOTES

The core of this first piece of analysis from the first set of site visits is *description* so that others can understand and make their own interpretations subsequently for a number of different purposes in the evaluation. There are a limited number of interpretative questions in what follows, but the emphasis is on establishing basic information on each site as perceived by each informant such as the objectives of the site, the key features of the setting, the organisational structure and the main tasks which have been accomplished so far. Sections where the interviewee's responses are required are clearly distinguished from those where the interviewer's interpretation/ view is asked for. As far as possible the analysis guide has been informed by the original objectives of the study as set out in the proposal. When all the site specific data are assembled it will be possible to undertake cross-case analysis with a view to seeing if a sensible classification of sites is possible for use in subsequent sampling, etc.

It is assumed that the interviewer has access to his/her detailed notes made during the interview as well as a recording of the interview. In the time likely to be available, the interviewer will probably listen through the tape once while amending and adding to the interview notes. The revised notes will have to serve as the basis for this first descriptive analysis. There will not be time for a detailed coding of interview transcripts followed by content analysis.

The writing-up of the interviews should be in the following format:

- 1. Respondent Details
- 2. Site Details
- 3. Interview Analysis (by key themes)
- 4 Post-Interview Details

The analysis framework that follows details the information required under these four headings.

PRE-INTERVIEW INFORMATION

RESPONDENT DETAILS

The respondent's details can be noted on the front of the interview guide before the interview takes place. Personal details concerning the background of the interviewee might be better obtained at the end of the interview. The respondent details should thus comprise the following:

Date and Place of the Interview

Name of the TP site

Name of the Respondent

Position held by the Respondent

Background of the Respondent

Name of the Interviewer

The first page of the interview report, therefore, will comprise these details.

SITE DETAILS (not necessary for all interviews)

The second section of the interview report will comprise details of the site itself. Much of this information will have been collected by checklist and the interviewee will check to make sure the following details of each site have been collected:

Number of practices in the site

Number of GP(s) in each practice in the site

Total patient population covered by the site

Number, and types, of other staff in the constituent practices

Services the site delivers on-site

Previous fundholding history (individual GPFHs, locality purchasers, multifund, etc)

Status of Health Agency (i.e. has the health authority merged with FHSA and/or with other health authorities and, if so, when).

Organisational Structure (in the form of a chart of internal management arrangements)

In addition, please list all the documentation that describes the site, its objectives, its purchasing intentions, and so forth, which has been produced to date. Copies of all this material should be lodged with the King's Fund Interview with the interview report.

ANALYSIS OF INTERVIEW BY KEY THEMES

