- 1. is the balance of care and choice of provider altered at pilot sites as compared with health authority purchasing (ie will TPPs make greater use of sources of care other than acute hospitals, eg use of alternative therapists; will TPPs adopt different priorities compared with health authorities?)
- 2. what effect does TP have on A&E attendances, emergency admissions, length of inpatient stays, day cases, outpatient referrals, investigations and prescribing?
- 3. to what extent are the activity changes associated with TP also associated with changes in the per patient costs of these services (ie do TPPs manage to make 'savings' in the costs of services)?
- 4. if cost reductions are shown, how are the freed up resources used by TPP sites?
- 5. does TP result in changes in activity by the primary health care team (eg an increase in GPs' availability to patients or access to services such as minor injuries clinics in order to avert hospital utilisation?)?
- 6. how closely do the objectives and business plans of the TPP sites correspond with the changes in activity patterns observed in practice?
- 7. to what extent are the changes in the nature or location of activity purchased by TPP sites a response to the needs, views and /or experiences of patients?
- does TP produce improvements in indicators of the quality of the process of health care (eg outpatient and inpatient waiting times, the speed with which test results and discharge summaries are made available) greater than those in SFH practices?

The fourth objective of the evaluation, and, in many ways the most important in a strategic sense, is to assess the effectiveness of TP through the benefits to patients. Given the timescale of the evaluation (October 1995 - September 1997), prospective data collection will only be possible on a maximum of 12 months before and after TP. The vast majority of TPP sites will only start purchasing in April 1996 with 1995/6 as a preparatory year. In this time, it is likely that any overall changes in patient outcomes will be modest and detecting them would require access to infeasibly

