large samples of patients. Instead, the primary focus will be on patients' experiences of services in four carefully selected sets of circumstances - A&E attendances, dependent people with complex needs requiring access to a range of community care services, people with severe mental illness and users of maternity services. Full descriptions of these elements in the overall evaluation are not included in this protocol since they are the subject of separate contracts with the Department of Health, although they are fully integrated in research terms with the evaluation as a whole. Protocols for these studies are available from [name] at the King's Fund Policy Institute, on request. The studies of maternity services and mental illness services include comparisons between TPPs, extended SFH and SFH populations. The A&E study is at present limited to a feasibility exercise. A decision as to whether to fund a full study will be taken in mid-1996.

Patients' experiences will be studied in terms of their level of involvement, and degree of choice as to what is provided for them, the appropriateness of their care and their views about TP. Outcome data will be collected over a 12-month period but it is unlikely that sufficiently large changes will be observed for any clear conclusions to be drawn.

In the case of people with serious mental illness and those requiring community care in order to maintain their quality of life in the community, an important question is whether consortia of GP practices can develop the expertise and relationships with providers and social services to act as purchasers and individual 'case managers' for vulnerable people and their carers who often have complex, multiple social and health care needs which straddle health and social services and who may require a changing combination of primary, secondary and domiciliary support over time. The coherence of the care 'packages' which TPPs secure for their patients, the gaps in their provision and the continuity of care which their patients experience will be indicators of the success with which the pilots tackle this aspect of their new roles. Other aspects which may be influential include their ability to balance the needs of patients with different severities of ill-health and to ensure that particular sorts of needs are not overlooked.

3: DESIGN OF THE EVALUATION OF TOTAL PURCHASING PILOT SITES

THE INTERVENTION AND ITS CONTEXT

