Sites are in varying states of readiness. This means that the more advanced ones made changes associated with TP ahead of the April 1995 start date. Some sites will begin to act as genuine purchasers gradually throughout 1995-96, while others are likely to spend the whole of 1995-96 in preparation for purchasing in 1996-97. In addition, it must be remembered that HCHS purchasing and general practice/primary care are themselves undergoing significant changes and will continue to do so during the life of the evaluation.

All these features pose problems for design and interpretation of an evaluation. They indicate that some caution will have to be exercised in interpreting any changes which are observed as due to TP even when a controlled before-and-after design is adopted.

CHOICE OF COMPARISONS TO BE MADE

Parts of the study where data are available for all practices

For some aspects of the evaluation, all total purchasing sites will be studied. These include the nature of services being purchased, relationships with health commissions etc (see section 4, below). In these parts of the study, the unit of both data collection and analysis will be the site rather than the individual practice, although there will be limited opportunity to examine variation within sites. In relation to services purchased, comparisons in these areas will be able to be drawn between what the TP sites are doing, and what their host health commissions are doing on behalf of the patients of non TP practices.

For the routine data on referrals, admissions and length of stay (see section 5, below), the unit of analysis will be the individual practice. Certainly no attempt should be made to analyse by individual referring GP because these data are unreliable. Because data are available by practice, there will be an opportunity to analyse differences within sites and between sites as well as differences between TP sites and reference practices (see below). Use should be made of this opportunity, since within site variation may be large.

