In addition, the component of the overall evaluation in which routine activity data are analysed (see Section 5.1, above) will provide information from the Hospital Episode Statistics (HES) system in England and equivalent data in Scotland on the extent to which all TPP sites which choose to contract separately for A&E and emergency care alter the type, volume and length of stay of emergency admissions as defined in HES.

The description which follows concentrates on the design of a component of the national evalution which focuses specifically on A&E/emergency care. This is in two main parts; one on A&E attendances; and, the other on emergency admissions. It is dependent on carrying out a preliminary feasibility study as explained above.

FEASIBILITY STUDY

Method

From the initial data collected from all TPP sites in summer 1995 as part of the 'core' process evaluation (section 4), sites intending to purchase accident and emergency care separately from the health authority will be identified. Also identified will be: the type of contracts (eg block, cost and volume) to be used; the major provider of A&E care for each TPP; and the TPP sites which intend to makes a priority of purchasing A&E care.

Further investigation will be needed to establish for TPP sites which intend to contract separately for A&E:

the nature of the contracts involved and the information on which the budgets were based;

the presence or absence of other specific potential confounders at each site;

the quality of the information systems in the A&E departments with which contracts are placed, and whether the necessary information can be obtained in suitable format for evaluation;

local practices and conventions that may affect the completeness and coding of data on A&E attendances and emergency admissions;

the routes by which patients can be admitted as an emergency (see figure 7.1)

local definitions of an 'emergency' admission

the quality of the information systems of the GPs using these A&E departments

availability of other forms of A&E provision locally, such as minor injuries clinics, and any plans to increase availability of these.

Resources and timetable

Because of the need to commence the main study (see below) not later than January 1996, it is anticipated that data will be collected for as many TPP sites as possible which intend to contract separately for A&E by the end of November 1995.

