method of referral (eg self or GP; local definitions to be clarified)
method of transport to A&E
time first arrived in A&E
time first seen
time of exit
disposal (eg admission or home)
letter to the GP

Other less crucial but nonetheless desirable information would include:

ethnicity postcode time of day examined professional examined by diagnostic tests

If the extent to which patients receive accident and emergency care in hospital without attending a casualty department (eg a minor injuries unit) is of concern, a prospective system will be set up, with clinicians recording the basic patient details. It is not possible to be more precise about this until local practices are identified. Where specific alternative sources of care have been set up such as minor injury clinics, activity data for these will also be sought. Changes in the use of A&E services will be interpreted in the light of such services or new approaches to care developed by the TPP practices (obtained from the 'core' project).

Where TPP practices have their own information on the number of A&E attendances by hospital in the pre- and post-TP periods, this will be used to check where patients of TPPs are attending for A&E care, and to validate the data collected from the A&E sites.

Number of sites to be analysed

The number of sites analysed will depend upon the adequacy of data on A&E attendances where, if the routine data are adequate and can be downloaded for analysis, it will be possible to examine detailed time series of attendances. Data will also be collected from as many of the A&E departments which the TPP patients attend for A&E as have adequate computerised data. The introduction of variable-cost A&E contracts may well be preceded, or at least accompanied, by improvements in A&E and GP data systems. For A&E departments with good data, information on all patients will be collected, starting at least four months before the introduction of TP, and continuing for 15 months.

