The dependent variables will mainly be proportions. Analyses will involve between-group comparisons of proportions with confidence intervals, and if there are sufficient data on potential confounders, logistic regression.

Consent

This project will be discussed fully with relevant parties including A&E staff, hospital managers, reference and TPP practice staff and Local Medical Committees where appropriate. Ethical committee approval will be obtained where required.

Schedule

September- November Feasibility study

December 1995 Researcher in post

Pilot manual data collection if necessary

January 1996 Begin pre-intervention audit/data collection at A&E sites

March 1996 End pre-intervention data collection

January 1997 Begin post-intervention data collection

March 1997 End post-intervention data collection

Oct 1997 Analysis and report complete

NATIONAL EVALUATION OF TOTAL PURCHASING PILOT SCHEMES 1995-1997

SERVICE PROVISION AND OUTCOMES FOR SEVERELY MENTALLY ILL PEOPLE

7.3

EVALUATION OF THE IMPACT OF

TOTAL PURCHASING and STANDARD GP FUNDHOLDING PLUS MENTAL ILLNESS IN-PATIENT TREATMENT

ON SERVICE PROVISION AND OUTCOMES FOR SEVERELY MENTALLY ILL PEOPLE .

from the National Primary Care Research and Development Centre, based at Manchester.

[name], Professor of Epidemiology and Public Health [name], Professor of General Practice [name], Senior Lecturer in Community Psychiatry

15th Nov 1995

ABSTRACT

A study of service provision and patient outcomes for mentally ill people is proposed, comparing Total Purchasing sites (TP), GP fundholding sites extended to include inpatient treatment for mental health problems (GPMH) and GP fundholding sites as originally conceived (GPF). Basic information will be obtained from all the TP and GPMH sites (by means of data from routine sources, questionnaires and telephone interviews), supplemented by more detailed information from a sample of Total Purchasing sites, GPMH practices and reference GP fundholders.

The proposed study is in four sections focusing on: services provided, outcomes in terms of accessibility and quality, the work of professional staff, and the impact of total purchasing on service costs and efficiency. In the first instance, comparisons will be made between the initial position and the situation which has developed after the first year of total purchasing. Longer follow-up would give much more information about change but resources are not available for this at present.

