comparison is beyond the scope and budget of this proposal but some data on direct service use are required to inform the economic analysis.

Assessment instruments

A trained and experienced senior researcher will use a semi-structured approach to addressing the relevant questions. The interview exercise will be repeated after 12 months, again giving the opportunity to examine longitudinal changes. A final decision has not yet been taken on whether these interviews will take place on a one to one basis or in groups.

STUDY 3: THE IMPACT OF PURCHASING DECISIONS ON THE WORK OF PRIMARY CARE TEAMS AND SPECIALIST MENTAL HEALTH WORKERS

This section will address the following question, based on the CPNs working in relation to the selected sample of TP, GPMH and reference sites, with follow-up at one year:

* Are the mental health nurses targeted more explicitly on the most severely mentally ill people?

Methods

CPN working with mentally ill people on the practice lists at the selected TP, GPMH and reference sites will be identified at visits to the practices. The staff will be interviewed at their practice site twice, during Spring and Summer 1996, and one year later.

As in Study 1, questions will address the balance of use of resources within practices including purchasing from providers and buying in staff to work in the practices. However, more detailed information will be collected from staff, and may include some detailed collection of workload data. It is important that this section of the study addresses all mental health problems, not just those related to severely mentally ill people, as different purchasing models may alter the balance of CPN care committed to serious and less serious forms of mental illness.

Sample size

The data collection and analysis for this study will be mainly descriptive. Since a deliberate decision has been made to study a small number of sites in greater depth, the power of this study to detect quantitative differences in workload will be limited.

Assessment instruments

Interview schedules will be prepared for the mental health nurses, relating to their work and to patients whom they see. These will be based on the work of [name] who also works with the National Centre in Manchester.

STUDY 4: IMPACT OF TOTAL PURCHASING ON SERVICE COSTS AND EFFICIENCY

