The field work would begin in January 1996, related to the lead-in period for Total Purchasing, for visiting GPMH practices and establishing a baseline for Total Purchasing and reference sites. Visits to the providers on the one hand, and to stakeholder groups on the other, would be spread evenly over the 18 months after April 1996, giving a 12 month follow-up for the various sites which would be entered into the study in a staggered manner. Time for analysis would also be allowed within the on-going survey work. The final writing up would occupy the last 3 months of the 2 year study.

Identical methods would be used to study standard fundholding which was extending to include mental illness in-patient treatment. Therefore there would be economies of scale and the time frame would also be identical.

The present funding proposal is for two years. The power of the study to detect differences between the purchasing models will be considerably enhanced if funding becomes available for an additional year, as this will give more time for service reconfiguration to take place.

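### The A&E timetable contradicts itself: with funding decided only in mid-1996, the January–March 1996 baseline for A&E attendances cannot be collected prospectively, and no retrospective route is specified

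*Protocol*

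**What the plan says.** **Start of TP.** Section 2 (fourth objective): "The vast majority of TPP sites will only start purchasing in April 1996 with 1995/6 as a preparatory year". Section 3 adds a qualification: "Some sites will begin to act as genuine purchasers gradually throughout 1995-96".

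**A&E, in the A&E proposal.** The main comparison is before against after the introduction of TP, between patients of TPP and reference practices. The feasibility section gives the reason for its own deadline: "Because of the need to commence the main study (see below) not later than January 1996". The Schedule has "January 1996 Begin pre-intervention audit/data collection at A&E sites", ends that collection in March 1996, and places post-intervention collection in January–March 1997. For departments with good computerised data, the section on the number of sites takes all attendances, "starting at least four months before the introduction of TP, and continuing for 15 months".

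**A&E, in the main protocol.** Section 2 says the A&E work is for now a feasibility exercise: "A decision as to whether to fund a full study will be taken in mid-1996". Table 8.1, in both places where it is printed, dates A&E data collection April 1996 to March 1997. Section 5.1 (Method) explains that A&E use is studied separately because routine activity data are lacking.

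**Mental health.** For the CPNs in Study 3: "The staff will be interviewed at their practice site twice, during Spring and Summer 1996, and one year later". The funding and timetable section says that visits to providers and stakeholder groups "would be spread evenly over the 18 months after April 1996, giving a 12 month follow-up for the various sites". The same section starts fieldwork in January 1996 to set a baseline for TP and reference sites. Study 1 compares admissions and length of stay in April 1995–March 1996 with April 1996–March 1997.

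**The concern.** A before-and-after comparison with concurrent controls needs a measurement before the change in both groups. TPP sites volunteered and reference practices are matched on only a few characteristics, so the pre-period is what separates an effect of TP from a difference that was already there. The effect on A&E attendances is one of the questions listed under the third objective, which specifies exactly this design.

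If the main protocol's dates are followed and nothing else is said, the before subgroups of the A&E study are not collected as planned. The attendance analysis could then become a post-only comparison of self-selected sites. Baseline weeks that pass unobserved cannot be repeated, so the protocol has to say in advance how they would be recovered.

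The mental-health fieldwork raises a smaller question of the same kind: whether its first interviews measure the position before TP or the first months of it.

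**Working it through.** No sample-size formula is involved. The check places each stated date in months from 1 April 1996 (month 0). Mid-1996 is read as June–July.

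| Item | Source | Months from go-live |
|---|---|---|
| A&E main study must start | A&E proposal, feasibility section | −3 or earlier |
| A&E baseline collection | A&E proposal, Schedule | −3 to 0 |
| A&E computerised data begin | A&E proposal, number of sites | −4 or earlier |
| A&E funding decision | Section 2 | about +2 to +3 |
| A&E data collection | Table 8.1 (both versions) | 0 to +12 |
| Mental-health site fieldwork begins | Mental-health timetable | −3 |
| Mental-health admissions data | Mental-health Study 1 | −12 to 0, then 0 to +12 |
| First CPN interviews | Mental-health Study 3 | mostly 0 to about +5 |
| Provider and stakeholder visits | Mental-health timetable | 0 to +18 |

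**A&E.** The funding decision comes 5 to 6 months after the start that the A&E proposal requires (−3 to +2, or −3 to +3). Collection as dated in Table 8.1 begins at month 0. Prospective months available before go-live are therefore 0 of the 3 in the Schedule.

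**Would the January–March 1996 window have been long enough?** The plan assumes at least 30,000 attendances per department per year and a target of 200 patients per subgroup. Weeks needed = 200 / (30,000 × coverage / 52).
- Coverage 40%: 200 / 230.8 = 0.87 weeks (plan: about one).
- Coverage 10%: 200 / 57.7 = 3.47 weeks (plan: about four).

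The plan's figures are reproduced. Three months is ample, so the fault lies in when the study can start and not in the length of the window.

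**Three or four months.** The Schedule gives three months before go-live. The four-month minimum applies only to departments with good computerised data, so this is a detail to align and not a clear conflict.

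**Mental health.** If the 12-month repeat falls inside the 18-month window, first visits occupy 18 − 12 = 6 months, that is 0 to +6, averaging about +3 if evenly spread. CPN follow-up one year after Spring/Summer 1996 falls in Spring/Summer 1997, at about +12 to +17. Table 8.1 ends the CPN work at March 1997 (+12), so those dates also disagree.

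**The case against.** **The A&E plan itself is sound on this.** Its Schedule puts the baseline before go-live. That is correct, and the defect is the conflict with section 2 and Table 8.1. The full study was also not yet committed.

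**The date of collection is not the date of the data.** A&E items are expected to be recorded routinely, and would be downloaded or taken from paper records. Admissions come from the patient administration system, casualty records and ward books. A late decision does not erase the January–March 1996 records. This stands, and it is why the problem can be repaired. It is only a partial answer. The A&E proposal calls computerised data variable in accuracy and completeness, and it nowhere specifies retrospective baseline collection. Recording for minor-injury care would be prospective, and some admission routes may be learned from the patients themselves.

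**Emergency admissions have another source.** Section 5.1 sets HES baselines from 1993/94 to 1995/96. This stands, so the gap concerns attendances.

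**The mental-health study has a baseline where it claims one.** Admission rates, the only outcome there with a power calculation, have a full prior year. The sentence claiming change before and after sites held budgets closes Study 1 and does not describe the CPN or stakeholder work. Provider interviews claim only the start-up period against one year later. A few CPN interviews might fall in March. All of this stands and makes the mental-health part secondary.

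**Conclusion.** The A&E timetable is wrong as written. The January 1996 start and January–March 1996 baseline cannot coexist with a mid-1996 funding decision and collection dated from April 1996. Under the later dates, none of the three planned months of attendance baseline can be collected prospectively, and no routine source replaces it.

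A reader might go further and infer that the A&E and mental-health studies have no true baseline at all. The documents do not support that. A&E records can in principle be retrieved later, emergency admissions have HES data, and the mental-health study has both a 1995/96 utilisation baseline and site fieldwork from January 1996. The CPN, provider and stakeholder contacts do fall mostly after go-live.

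A reader might also want to state what share of the effect those late first contacts would miss. No such figure is supportable. It would require an effect that stops growing at month 12, whereas a first contact at +3 is followed up at +15 and section 3 expects most contracts to be largely unaltered in the first year. The interviews are also mainly qualitative.

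The conclusion assumes April 1996 as go-live. Section 3 concedes that some sites purchased earlier, so for them even a January–March 1996 baseline is not clean.

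**What to change.** **A&E.**
- Reconcile section 2, Table 8.1 and the A&E Schedule. State that, if the full study is funded, the January–March 1996 baseline will be abstracted retrospectively from A&E computer or paper records and the patient administration system, for TPP and reference patients alike, matched to January–March 1997.
- Date the Table 8.1 data period from January 1996, and from at least four months before TP where the computerised route applies.
- State which items will have no baseline because they need prospective capture, such as minor-injury recording and routes obtained from patients.

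**Mental health.**
- Anchor the first CPN interviews to a caseload snapshot at 31 March 1996 where records allow. Otherwise report the CPN, provider and stakeholder parts as early TP against later TP, not as before and after. Moving all first contacts into January–March 1996 is doubtful, with one full-time research assistant and special-interest sites still being identified.
- Reconcile the March 1997 end date in Table 8.1 with follow-up in Spring/Summer 1997.

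**Cost.** A timetable amendment and a few sentences of method. The abstraction uses records the A&E study already planned to use. It depends on the GP field being complete enough to separate TPP from reference patients, which the feasibility work can check.
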